6.4.5 Analysis of neutralization activity and correlation with serum concentrations

6.4.5.1 Primary analyses of neutralization magnitude-breadth (MB) curves

To address primary objective 3, at each specified timepoint, the area under the magnitude-breadth curve (AUC-MB) to a global panel of pseudoviruses (58) will be computed for each participant in the PP cohort with evaluable neutralization ID₅₀ or ID₈₀ data, as described in (59). Magnitude-breadth (MB) curves will be employed to display individual- and group-level response breadth as a function of magnitude. Response breadth is defined as the percentage of viruses in the panel with neutralization titer above certain thresholds. Comparisons of the MB curves among arms will be based on a nonparametric Wilcoxon rank sum test on the participant-specific AUC-MB and a Kolmogorov-Smirnov type test on the group-average MB curves. Simulations will be used to obtain two-sided p-values for the latter test. An alternative approach based on constructing a weighted-average score-like variable will be explored. Details of either approach will be described in the SAP.

6.4.5.2 Secondary analyses of correlations between serum concentrations and serum neutralization levels

To address secondary objective 1, pharmacodynamics (PD) models based on either linear or nonlinear mixed effects models will be performed to characterize the correlation between serum concentration (observed or population pharmacokinetic [popPK] model-predicted) and serum neutralization against each virus or the AUC-MB of serum neutralization against the panel. Data from all enrolled participants will be analyzed regardless of how many administrations and how much mAb dose they received (MITT analysis). Similar to the popPK analysis, data from specimens collected outside of the visit window may be included in the PK/PD analyses that account for the actual specimen collection time and the actual time and dose amount of each product administration. Since the exact date of HIV acquisition is unknown, any serum-level data from blood draws 4 weeks prior to a participant living with HIV's last seronegative sample and thereafter may be excluded. All data from participants living with HIV who have no seronegative samples postenrollment may be excluded from the analysis.

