5.1 Primary objectives and endpoints

Primary objective 1:

To evaluate the safety and tolerability of VRC01.23LS when administered alone via IV route (Part A) and of VRC01.23LS + PGT121.414.LS + PGDM1400LS, when administered consecutively via IV route (Part B)

Primary endpoints 1:

- Local and systemic solicited AEs, laboratory measures of safety, unsolicited AEs, and SAEs
- Early discontinuation of administration and reason(s) for discontinuation and early study termination

Primary objective 2:

To evaluate the serum concentrations and PK of VRC01.23LS when administered alone via IV (Part A) and of VRC01.23LS + PGT121.414.LS + PGDM1400LS after consecutive administration via IV route (Part B)

Primary endpoint 2:

Serum concentrations of VRC01.23LS, PGT121.414.LS, and PGDM1400LS at prespecified timepoints among participants who received all scheduled product administrations

Primary objective 3:

To evaluate the individual mAb-specific serum neutralizing activity of VRC01.23LS when administered alone via IV route (Part A) and of VRC01.23LS + PGT121.414.LS + PGDM1400LS, after consecutive administration via IV route (Part B)

Primary endpoint 3:

Magnitude of serum neutralizing activity measured with mAb-specific Envpseudotyped viruses in TZM-bl cells at prespecified timepoints among participants who received all scheduled product administrations

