6.1.3 Sample-size calculations for serum neutralization activity

Primary objective 3 of this study is to evaluate serum neutralization titers of VRC01.23LS against Env-pseudotyped viruses specific to VRC01.23LS at several timepoints following IV administration of VRC01.23LS and of VRC01.23LS, PGT121.414.LS, and PGDM1400LS against Env-pseudotyped viruses specific to each mAb at several timepoints following consecutive IV administrations. This objective is also descriptive, and will be accomplished by estimating the mean serum neutralization titers of each mAb against the specific virus within each treatment group. The precision with which a true mean neutralization titer can be estimated from observed data depends on the SD of the measurements and the sample size. Table 6-3 summarizes two-sided 95% CIs for

the mean neutralization titer for selected values of the observed average infectious dose ID50 or ID80 neutralization titer. The construction of these CIs assumed sample sizes of n = 6 or n = 24, reflecting an attrition rate of 20% compared to the planned treatment group size of 8 or 30 participants in Part B, respectively. The calculations assumed that log-transformed neutralization titers are approximately normally distributed. To account for the small sample sizes, a t-distribution was used to construct CIs. For instance, with an observed mean titer of $\log_e(50)$ and assuming an SD of 0.5 for their log-transformed values, a two-sided 95% CI for the true mean neutralization titer is (29.6, 84.5) and (40.5, 61.8) with an effective sample size of 6 or 24 participants. Of note, based on neutralization data against a global panel of 11 pseudoviruses in 6 participants in HVTN 104, an SD of approximately 1.0 was observed in the log-transformed ID50 titers at various timepoints post–IV infusions of VRC01 (57).

Table 6-3 Two-sided 95% CIs based on observing a particular average $log_{e^{-}}$ neutralization titer in n = 6 or n = 24 participants in 1 treatment arm, considering 20% attrition of n = 8 or n = 30 participants

Observed average log _e neutralization titer	SD of log _e neutralization titer	95% CI n = 6	95% CI n = 24
log _e (10)		(5.9,17)	(8.1,12)
$\log_{e}(50)$		(30,85)	(40,62)
log _e (100)	0.5	(59,169)	(81,124)
log _e (500)		(296,845)	(405,618)
log _e (1000)		(592,1690)	(810,1235)
log _e (10)		(3.5,29)	(6.6,15)
$\log_{e}(50)$		(18,143)	(33,76)
log _e (100)	1.0	(35,286)	(66,153)
log _e (500)		(175,1428)	(328,763)

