10.4 Neutralizing antibody (nAb) assay

HIV-1–specific nAb assays will be performed on serum samples from study participants taken at postadministration timepoint(s) and at baseline. The TZM-bl assay will test neutralization of mAb-specific viruses (1 virus per mAb). The assay will also test the neutralization of a panel of viruses that exhibit a range of known sensitivities to VRC01.23LS, PGT121.414.LS, and PGDM1400LS. The viruses will be selected from a global and/or clade-specific panel (58, 64) and may be modified by site-directed mutagenesis to be capable of measuring the activity of each mAb individually.

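### Section 6.4.5.1 addresses primary objective 3 with a global-panel AUC-MB, which is not primary endpoint 3 and contradicts Section 6.1.3

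*Protocol*

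**What the plan says.** Four places in the protocol bear on primary objective 3.

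- **Section 5.1.** The objective is the activity of each individual mAb. Its endpoint is "Magnitude of serum neutralizing activity measured with mAb-specific Envpseudotyped viruses in TZM-bl cells at prespecified timepoints", among participants who received every scheduled administration.
- **Section 10.4.** The assay uses one mAb-specific virus for each mAb. A broader panel, with a range of sensitivities to the three mAbs, is listed as a further test.
- **Section 6.1.3.** The objective is called descriptive and "will be accomplished by estimating the mean serum neutralization titers of each mAb against the specific virus within each treatment group". Table 6-3 gives 95% confidence intervals for that mean.
- **Section 6.4.5.1.** This is the only primary neutralization analysis in Section 6.4. It begins "To address primary objective 3, at each specified timepoint, the area under the magnitude-breadth curve (AUC-MB) to a global panel of pseudoviruses", computed per participant in the per-protocol cohort from ID50 or ID80 data. It continues: "Comparisons of the MB curves among arms will be based on a nonparametric Wilcoxon rank sum test on the participant-specific AUC-MB", together with a Kolmogorov-Smirnov type test on the group-average curves. It does not mention the mAb-specific viruses.

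The combined magnitude and breadth of the three mAbs is secondary objective 2 (Section 5.2), which has its own AUC-MB analysis in Section 6.4.5.3.

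**The concern.** The analysis labelled as answering primary objective 3 does not use the variable that defines primary endpoint 3. It also conflicts with Section 6.1.3 on the variable (panel AUC-MB against single-virus titer) and on the kind of analysis (between-arm tests against within-group estimation).

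The difference matters most in Part B. All 62 participants there (4 × 8 + 30) receive three mAbs, so any panel virus sensitive to more than one of them returns a combined response. A panel summary of that serum is close in kind to secondary objective 2. It does not isolate the activity of one mAb, which is what the objective asks for. An SAP written from Section 6.4.5.1 departs from Sections 5.1 and 6.1.3, and one written from Section 6.1.3 departs from Section 6.4.5.1.

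**Working it through.** **1. What Table 6-3 is sized for.** Inputs from Section 6.1.3: effective n of 6 and 24 (20% attrition from 8 and 30: 8 × 0.8 = 6.4, 30 × 0.8 = 24), SD of the log titer 0.5 or 1.0, and a t-based two-sided 95% interval on the natural-log scale.

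Formula: exp{log(m) ± t(0.975, n − 1) × SD/√n}.

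For m = 50 and SD = 0.5:

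- n = 6: 2.571 × 0.5/√6 = 0.525, a factor of 1.69, giving (29.6, 84.5).
- n = 24: 2.069 × 0.5/√24 = 0.211, a factor of 1.235, giving (40.5, 61.8) to rounding.

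Both match the figures in Section 6.1.3. At SD 1.0 the factors are 2.86 and 1.53, and for m = 1000 they give (350, 2856) and (656, 1525), as tabulated. The sizing is therefore a one-sample interval for a mean log titer. The protocol states no precision for AUC-MB and no power for the between-arm tests.

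**2. The two accounts side by side.**

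| | Sections 5.1, 6.1.3 and 10.4 | Section 6.4.5.1 |
|---|---|---|
| Virus | One specific virus per mAb | Global panel |
| Variable | Titer | AUC-MB per participant |
| Analysis | Descriptive mean by group | Between-arm rank and curve tests |
| What it measures in Part B | Each mAb | All three mAbs together |
| Precision stated | Table 6-3 | None |

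**3. Why a combined response can mask one mAb (illustration only).** Assumptions: titers add, so the combined titer is the sum of concentration/IC80 over the three mAbs, and each mAb is at 100 mcg/mL. The IC80s are the sensitive-virus medians in Table 4-6: VRC01.23 0.107, PGT121.414.LS 0.051, and PGDM1400 0.047 standing in for PGDM1400LS. The protocol's own projections use a Bliss-Hill model, so this is a simplification.

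- Virus sensitive to all three: 934.6 + 1,960.8 + 2,127.7 = 5,023.
- VRC01.23LS activity halved: 467.3 + 1,960.8 + 2,127.7 = 4,556, a fall of 9%.
- PGT121.414.LS activity halved instead: 934.6 + 980.4 + 2,127.7 = 4,043, a fall of 20%.
- Virus sensitive to VRC01.23LS only (IC80 of 50 mcg/mL assumed for the other two): 934.6 + 2 + 2 = 939. With VRC01.23LS halved: 467.3 + 2 + 2 = 471, a fall of 50%.

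The same two-fold loss shows in full on a virus specific to that mAb and is diluted on a virus that all three neutralize.

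**The case against.** The strongest reply is that the protocol does plan the right analysis. Section 6.1.3 commits to the mean titer of each mAb against its own virus in each group, with t-based intervals sized on the Part B groups. Section 10.4 plans the assay, Section 6.4.7 provides by-arm summaries of continuous assay data, and Section 6.4.5.2 models neutralization against each virus or the panel AUC-MB. This stands. A reader might infer that mAb-specific activity goes unanswered in Part B, or that no analysis of endpoint 3 exists; the documents do not support either.

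A reader might also infer that the panel metric is dominated by VRC01.23LS and nearly blind to the other two mAbs. In Figure 4-7 at Week 12, going from 40 + 5 + 5 to 40 + 40 + 40 mg/kg moves combined coverage only from 97% to 100% (clade B) and from 87% to 96% (clade C). That inference fails for three reasons.

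- Figure 4-7 counts modelled titers above a single threshold, near its ceiling, against viruses from an earlier trial's control arm. AUC-MB keeps magnitude and uses a different panel. Under the additive illustration, the same 8-fold rise lifts the titer on a triple-sensitive virus from 934.6 + 245.1 + 266.0 = 1,446 to 5,023, about 3.5-fold.
- At Week 24 the same rows move from 83% to 88% and from 72% to 85%. The Week 12 clade labels for the highest dose are also reversed in Section 4.2.1.
- Table 4-6 gives PGT121.414.LS and PGDM1400 lower median IC80s than VRC01.23 on sensitive viruses.

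Nor would a loss of activity necessarily go unseen. Concentrations are analysed separately for each mAb (Section 6.4.4.1), and ADA-positive samples go to a functional assay (Section 10.6). Section 10.4 also allows viruses to be modified to measure each mAb individually, but this is optional and Section 6.4.5.1 does not carry it over.

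The reply does not remove the conflict. Section 6.4.5.1 fixes the primary variable and defers to the SAP only the details of the panel approach.

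**Conclusion.** The point holds as a mis-specified primary analysis and an internal contradiction. Section 6.4.5.1 does not analyse primary endpoint 3, and it disagrees with Section 6.1.3 on both variable and type of analysis. This affects one of the three primary objectives. In Part B the panel AUC-MB cannot be read as the activity of one mAb and can mask a change in it. In Part A, where only VRC01.23LS is given, the result is attributable but is still the wrong endpoint.

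No planned figure is wrong: Table 6-3 is correct for the analysis in Section 6.1.3. How much masking would occur is not established, because the 9%, 20% and 50% falls rest on the assumed additive model and concentrations. The conclusion itself needs only the protocol text and the fact that Part B serum contains three mAbs.

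**What to change.** In Section 6.4.5.1, state as the primary analysis of objective 3 the geometric mean ID50 and ID80 titer against each mAb-specific virus. Report it by group and timepoint in the per-protocol cohort, with a t-based 95% confidence interval on the log scale, as Section 6.1.3 and Table 6-3 already assume. Describe it as descriptive.

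Keep the global-panel AUC-MB with its Wilcoxon and Kolmogorov-Smirnov type tests, but label it secondary under objective 2 or supportive. Secondary objective 2 concerns the three-mAb administrations, so the Part A panel results fit better as supportive. Section 6.4.5.3 uses all participants with evaluable data and a panel sensitive to all three mAbs, so the relabelled text should say which cohort and panel apply.

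The cost is wording in Section 6.4.5.1 and matching text in the SAP, settled before the neutralization data are analysed. The mAb-specific assays are already planned in Section 10.4. No specimen, assay or sample-size figure changes, and the Table 6-3 precision then applies to the primary analysis directly.

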6.4.5.3 Secondary analyses of neutralization MB curves

To address secondary objective 2, at each specified timepoint, the AUC-MB to a panel of Env-pseudotyped reference viruses that are sensitive to all 3 bnAbs will be computed for all participants with evaluable neutralization ID50 or ID80 data, as described in (59). MB curves may be employed to display individual- and group-level response breadth as a function of magnitude.

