5.2 Secondary objectives and endpoints

Secondary objective 1:

To correlate serum concentrations of VRC01.23LS, PGT121.414.LS, and PGDM1400LS with corresponding virus neutralization titers in serum

Secondary endpoints 1:

- Serum concentrations of VRC01.23LS, PGT121.414.LS, and PGDM1400LS at prespecified timepoints for all participants in all groups regardless of how many product administrations and how much product they received
- Magnitude of serum neutralizing activity measured with Env-pseudotyped viruses in TZM-bl cells at prespecified timepoints for all participants in all groups regardless of how many product administrations and how much product they received

Secondary objective 2:

To determine whether the mAbs maintain their expected combined magnitude and breadth of serum neutralizing activity after each 3-mAb administration as predicted by the known magnitude and breadth of neutralization of the corresponding mAb combinations as noninfused clinical products

Secondary endpoint 2:

Magnitude of neutralizing activity against a panel of Env-pseudotyped reference viruses in TZM-bl cells at selected timepoints for all participants in all groups regardless of how many product administrations and how much product they received

Secondary objective 3:

To determine whether ADAs are present and whether there is a correlation among VRC01.23LS, PGT121.414.LS, and PGDM1400LS concentrations and ADA titers in serum samples

Secondary endpoint 3:

Serum VRC01.23LS, PGT121.414.LS, and PGDM1400LS concentrations and ADA titers in each group measured at prespecified timepoints for all participants in all groups regardless of how many product administrations and how much product they received

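### Secondary objective 2 asks about combined magnitude and breadth, but Section 6.4.5.3 analyses it only on viruses sensitive to all three antibodies

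*Protocol*

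**What the plan says.** Four places in the Protocol bear on this point.

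- **Section 5.2, secondary objective 2:** "To determine whether the mAbs maintain their expected combined magnitude and breadth of serum neutralizing activity after each 3-mAb administration". The expectation comes from the known activity of the same combinations as products that have not been infused. The endpoint is "Magnitude of neutralizing activity against a panel of Env-pseudotyped reference viruses in TZM-bl cells at selected timepoints", in everyone in every group however much product they received. It sets no condition on which viruses enter the panel.
- **Section 6.4.5.3, the analysis of that objective:** "the AUC-MB to a panel of Env-pseudotyped reference viruses that are sensitive to all 3 bnAbs will be computed for all participants". No other panel is named for secondary objective 2, and no cut-off defines *sensitive*.
- **Section 10.4, the assay:** "The assay will also test the neutralization of a panel of viruses that exhibit a range of known sensitivities to VRC01.23LS, PGT121.414.LS, and PGDM1400LS". Panel members are drawn from global or clade-based sets. Engineered versions are allowed: a virus "may be modified by site-directed mutagenesis to be capable of measuring the activity of each mAb individually".
- **Section 6.4.5.1, the primary neutralization analysis:** "Response breadth is defined as the percentage of viruses in the panel with neutralization titer above certain thresholds". Here AUC-MB is computed on a global panel, for primary objective 3, in the per-protocol cohort, with comparisons between arms.

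**The concern.** Breadth is a proportion of panel viruses, so it depends on which viruses are in the panel. Section 4.1.1 gives the reason for combining the antibodies: VRC01.23LS is very broad, and the other two are narrower but more potent and complement it. Complementary coverage shows on strains that one or two of the antibodies neutralize and the rest do not. A panel of viruses that all three neutralize contains none of these.

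The magnitude half of the objective can still be studied on such a panel. The breadth half cannot be studied well. A statement that combined breadth held as predicted would rest on viruses chosen because each antibody already works on them, and could not be carried over to the wider set of strains for which the combination is intended.

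**Working it through.** **Inputs.** Table 4-6 gives the share of a 208-virus multiclade panel that each antibody neutralizes. It has a column for PGDM1400 but none for PGDM1400LS, so PGDM1400 is used as a stand-in (assumption). Section 6.4.5.3 gives no cut-off, so two are shown: IC80 and IC50 below 50 mcg/mL (assumption).

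**Step 1: reproduce the plan's figures.** Figure 4-14 gives counts for VRC01.23LS. At IC80 below 50, 200/208 = 96.2%. At IC80 below 1.0, 188/208 = 90.4%. These agree with the 96% and 90% in Table 4-6.

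**Step 2: share of viruses that could be sensitive to all three.** The table does not give the overlap, but the single shares a, b and c bound it:

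- lower bound = max(0, a + b + c − 2)
- upper bound = min(a, b, c)
- if sensitivities were independent = a × b × c

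| Cut-off (mcg/mL) | PGT121.414.LS | PGDM1400 | VRC01.23 | Lower | Independent | Upper |
|---|---|---|---|---|---|---|
| IC80 < 50 | 50% | 74% | 96% | 0.50 + 0.74 + 0.96 − 2 = 20% | 0.50 × 0.74 × 0.96 = 35.5% | 50% |
| IC50 < 50 | 58% | 80% | 96% | 0.58 + 0.80 + 0.96 − 2 = 34% | 0.58 × 0.80 × 0.96 = 44.5% | 58% |

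Of 208 viruses this is 42 to 104 (74 if independent) at IC80, and 71 to 121 (93 if independent) at IC50. The restriction therefore removes at least 50% of the panel at the first cut-off and at least 42% at the second.

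**Step 3: which viruses are removed.** Coverage by at least one antibody lies between max(a, b, c) = 96% and 100% at both cut-offs. Viruses covered by one or two antibodies, but not all three, then make up:

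- IC80 < 50: from 96 − 50 = 46% to 100 − 20 = 80% of the panel
- IC50 < 50: from 96 − 58 = 38% to 100 − 34 = 66% of the panel

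Nearly everything removed is a strain that the combination covers through only some of its components.

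**Step 4: is breadth on the restricted panel fixed at its ceiling?** No. Section 4.2.2 predicts about 10 mcg/mL of each antibody 24 weeks after 5 mg/kg each. With the predicted titer taken as concentration divided by IC80, a single-antibody titer above 200 needs an IC80 below 10/200 = 0.05 mcg/mL. The median IC80 among sensitive viruses in Table 4-6 is 0.051 (PGT121.414.LS), 0.047 (PGDM1400) and 0.107 (VRC01.23). About half or more of each antibody's sensitive viruses would sit near or below 200 for that antibody alone. The combined titer would be higher, but it would still vary with dose, time and threshold.

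**The case against.** The restriction has a scientific use. Endpoint 2 is worded as a magnitude, Section 4.1 asks whether combined antibodies act additively or synergistically, and three-way interaction or interference can be seen only on viruses that all three bind. This stands, and it is why the triple-sensitive set should be kept as a supporting analysis.

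The trial also looks at related questions elsewhere. Section 6.4.5.1 covers breadth on a global panel, and Section 6.4.5.2 relates concentration to neutralization in all enrolled participants. Neither sets combined breadth against prediction: the first compares arms in the per-protocol cohort, and the second models concentration against titer.

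A reader might infer more than the documents support:

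- *Breadth would be near 100% by construction.* It is defined on serum titer thresholds, not in vitro sensitivity, and step 4 shows that it can vary.
- *The objective would be met whatever happened.* No pass criterion is stated, and lost potency would lower AUC-MB.
- *A failing antibody would go unseen.* Primary objective 3 tests each antibody on its own virus, and each concentration is analysed separately.
- *Section 6.4.5.3 contradicts Section 10.4.* Triple-sensitive viruses could be a subset of that panel and still differ in IC80. The two sections do not match, but they are not strictly incompatible.
- *Figure 4-7 shows that only 8% (clade B) and 17% (clade C) of strains would qualify.* Those are shares with all three predicted titers above 200 at Week 12 under 40 + 40 + 40 mg/kg. They do not measure eligibility for the panel.
- *The comparison with prediction has been omitted.* Its method may properly sit in the statistical analysis plan, which is not at hand.

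**Conclusion.** The concern holds for the breadth half of secondary objective 2. The protocol itself fixes the restriction, so this is not a detail left for later. The panel in Section 6.4.5.3 is narrower than the endpoint in Section 5.2 and differs from the description in Section 10.4.

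On Table 4-6, 20% to 50% of the viruses could qualify at IC80 below 50 mcg/mL, and 34% to 58% at IC50 below 50 mcg/mL. The range rests on the assumed cut-off, on PGDM1400 standing in for PGDM1400LS, and on the 208-virus panel as a guide to whatever panel is assayed. The bounds need no assumption about how the sensitivities overlap; only the 35.5% and 44.5% figures assume independence.

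The consequence is limited to this secondary analysis. As written it can inform on magnitude and additivity, but says little about whether combined breadth is maintained.

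**What to change.** - In Section 6.4.5.3, compute AUC-MB and magnitude-breadth curves for secondary objective 2 on the Section 10.4 reference panel with its spread of sensitivities, in all participants, and set them against the breadth predicted from the non-infused products. The prediction model can be specified in the statistical analysis plan.
- Keep the triple-sensitive viruses as a supporting analysis of magnitude and of additivity or interference.
- Use the same panel wording in Sections 5.2, 6.4.5.3 and 10.4.

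Section 10.4 already plans to test the wider panel, so the cost is a wording change and modest extra analysis.
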